5.3.3. Escape Arm

Patients who require topical or systemic rescue treatment (Section 6.3) for atopic dermatitis during the Induction Period, or, are non-responders at Week 16, will be eligible for treatment in an Escape Arm where patients will receive lebrikizumab Q2W from Week 16 through Week 52. In addition, patients who do not maintain an acceptable response during the Maintenance Period (have an EASI score <50% of baseline), will be eligible for the Escape Arm.

To enter the Escape Arm, patients must have been compliant with study visits during the Induction Period or the Maintenance Period, respectively. Patients receiving systemic rescue medication (Section 6.3) will be required to washout for 5 half-lives prior to initiating treatment in the Escape Arm. All patients eligible for the Escape Arm will receive blinded loading doses, based on their prior treatment assignment (see Table 3 below), followed by 250 mg lebrikizumab Q2W through Week 52 on study in an open-label fashion. Patients in the Escape Arm must

comply with study visits every 4 weeks. Patients in the Escape Arm, not achieving or maintaining an EASI50 score after 8 weeks of treatment will be terminated from the trial.

Table 3: Escape Arm Dosing Schedule by Treatment Group

Induction Group Assignment	Maintenance Treatment Assignment	Maintenance Loading Dose (Blinded)	Week 20 to 50 (Unblinded: 250mg Q2W)
Patients entering Escape Arm at Week 16			
Active	Escape arm	Week 16: one active and one placebo injection Week 18: one active and one placebo injection	One active injection
Placebo	Escape arm	Week 16: two active injections Week 18: two active injections	One active injection
Patients entering Escape Arm at Week 24, 32, 40 and 48			
	Lebrikizumab 250 mg Q2W	At entry: one active and one placebo injection At next administration: one active and one placebo injection	One active injection
	Lebrikizumab 250 mg Q4W	At entry: one active and one placebo injection At next administration: one active and one placebo injection	One active injection
	Placebo	At entry: two active injections At next administration: two active injections	One active injection

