Section 4, Section 6.11	
 Added “Time to loss of EASI-75 in the subset of patients who were re-randomized and achieved EASI-75 at Week 16 (EASI-75 calculated relative to baseline EASI score)” Updated “Time to loss of EASI-50 in the subset of patients who were re-randomized and achieved EASI-75 at Week 16 (EASI-50 and EASI-75 calculated relative to baseline EASI score)” to “Time to loss of EASI-50 in the subset of patients who were re-randomized at Week 16 (EASI-50 calculated relative to baseline EASI score)” Added “Percentage change in EASI score from Baseline at Week 52 in the subset of patients who were re-randomized at Week 16 ” as a major secondary endpoint for EMA Moved “Percentage change in SCORAD (having achieved EASI-75 at Week 16) from baseline at Week 52” from major secondary endpoints to other secondary endpoints 	
Added to allow analysis on time to loss of EASI-75
 
Modified to allow analysis on time to loss of EASI-50 on patients who were re-randomized at Week 16 as an overall evaluation of how soon those patients will move to escape arm
 
To reflect the change in the strategy of multiplicity control for EMA

Section 6.3	
 Added specification of covariates to be adjusted for maintenance period analysis 	Clarification
Section 6.8	
 Patient demographic variables and baseline characteristics will be summarized by treatment group for the mITT Population, the Modified Maintenance Primary Population and the Modified Maintenance W16 Escape Population. 	Added to allow the comparison between responders and non-responders at Week 16 in terms of patient characteristics

	
 The number and percentage of patients with specific medical history events of interest pre-specified on the History Assessment eCRF (hand dermatitis, facial dermatitis, conjunctivitis, herpes Zoster, and others) will be summarized for the mITT Population, the Modified Maintenance Primary Population and the Modified Maintenance W16 Escape Population by treatment group and by treatment and age groups. 	

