5.1.3.2. Maintenance Escape Period

[figure not shown]
Patients who do not achieve an IGA of 0 or 1 or an EASI-75 at Week 16, patients received topical or systemic rescue therapy between baseline to Week 16 and those patients not

maintaining an EASI-50 response following re-randomization at Week 24, 32, 40, or 48 will be assigned to an Escape Arm and receive lebrikizumab 250 mg as open-label treatment Q2W through Week 52. Patients not achieving an EASI-50 response in the Escape Arm after 8 weeks of treatment will be terminated from the study.

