5.3. Method of Assignment to Treatment

All patients will be randomly allocated to receive the study treatment using an electronic data capture (EDC) system at the Baseline visit. The allocation to treatment will be prospectively stratified by geographic region (US versus EU versus rest of world), age (adolescent patients 12 to <18 years versus adults \geq 18 years) and disease severity (IGA 3 versus 4). At the Baseline visit (Day 1), once a patient is considered eligible to participate in the study, demographic and stratification information will be entered into the EDC system to receive a medication number assigning a kit to a patient.

During the Maintenance Period, the EDC will be used to re-randomize a patient to a maintenance treatment based on the IGA or EASI score at Week 16 and rescue therapy usage during induction period.

6. A Priori Statistical Methods

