Maintenance Secondary Population (MSP)	All patients who were randomized to placebo at Baseline Visit and re-randomized to Lebrikizumab 250 mg Q2W, Lebrikizumab 250 mg Q4W or placebo at Week 16, and received at least one dose of study treatment during the maintenance period .
Modified Maintenance Secondary Population (mMSP)	MSP Population excluding all patients from Site 5042. Patients will be analyzed according to the treatment to which they were re-randomized. Only information prior to escape will be presented. Selective efficacy analyses for the maintenance period will be conducted on the Modified Maintenance Secondary Population.
Maintenance W16 Escape Population	All patients who were NOT re-randomized to Lebrikizumab 250 mg Q2W, Lebrikizumab 250 mg Q4W or placebo but assigned to escape arm at Week 16, and received at least one dose of study treatment during the maintenance period .
Modified Maintenance W16 Escape Population	Maintenance W16 Escape Population excluding all patients from Site 5042. Selective efficacy analyses for the maintenance period will be conducted on the Maintenance W16 Escape Population.
Maintenance W24-48 Escape Population	All patients from Maintenance Primary and Secondary Population who escaped to Lebrikizumab 250 mg Q2W due to EASI-50 non-response at Week 24, 32, 40 or 48.
Modified Maintenance W24-48 Escape Population	Maintenance W24-48 Escape Population excluding all patients from Site 5042. Selective efficacy analyses for the maintenance period will be conducted on the Maintenance W24-48 Escape Population
All Lebrikizumab Safety Population	All randomized patients who received at least 1 dose of lebrikizumab treatment during Combined Induction and Maintenance Periods .

All Lebrikizumab Modified Safety Population	All Lebrikizumab Safety Population excluding all patients from Site 5042. Safety analyses for the Combined Induction and Maintenance Periods will be conducted on All Lebrikizumab Modified Safety Population. Selective safety analyses for the Combined Induction and Maintenance Periods plus the follow-up Period will be conducted on All Lebrikizumab Modified Safety Population.
---	--

Abbreviations: EASI = Eczema Area and Severity Index; IGA = Investigator Global Assessment.

Table KGAC.6.2. Treatment Groups and Comparisons for Each Study Period and Analysis Population

Study Period	Analysis Population	Treatment Groups	Abbreviation	Inferential Comparisons When Applicable

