Induction Period	mITT; Modified Safety; Safety	Placebo; Lebrikizumab 250 mg Q2W	PBO; LEB250Q2W	LEB250Q2W vs PBO
Maintenance Blinded Period	Modified Maintenance Primary; Maintenance Primary (Safety analysis only)	Lebrikizumab_Res/Placebo; Lebrikizumab_Res/Lebrikizumab 250 mg Q4W; Lebrikizumab_Res/Lebrikizumab 250 mg Q2W; Total Lebrikizumab_Res/ Lebrikizumab (Safety analysis only)	LEB_Res/PBO; LEB_Res/LEB250Q4W; LEB_Res/LEB250Q2W; Total LEB_Res/LEB (Safety analysis only)	LEB_Res/LEB250Q4W vs LEB_Res/PBO; LEB_Res/LEB250Q2W vs LEB_Res/PBO
Maintenance Blinded Period	Modified Maintenance Secondary	Placebo_Res/Placebo; Placebo_Res/Lebrikizumab 250 mg Q4W; Placebo_Res/Lebrikizumab 250 mg Q2W	PBO_Res/PBO; PBO_Res/LEB250Q4W; PBO_Res/LEB250Q2W	No Between-Group or Overall Comparisons
Maintenance Escape Period	Modified Maintenance W16 Escape	Lebrikizumab_NonResp/ Lebrikizumab 250 mg Q2W; Placebo_NonResp/Lebrikizumab 250 Q2W	LEB_NonResp/ LEB250Q2W; PBO_NonResp/ LEB250Q2W	No Between-Group or Overall Comparisons
Maintenance Escape Period	Modified Maintenance W24-48 Escape	Lebrikizumab 250 mg Q2W/Placebo/ Lebrikizumab 250 mg Q2W; Lebrikizumab 250 mg Q2W/Lebrikizumab 250 mg Q4W/Lebrikizumab 250 mg Q2W; Lebrikizumab 250 mg Q2W/Lebrikizumab 250 mg Q2W/Lebrikizumab 250 mg Q2W; Placebo/Placebo/Lebrikizumab 250 mg Q2W; Placebo/Lebrikizumab 250 mg Q4W/Lebrikizumab 250 mg Q2W; Placebo/Lebrikizumab 250 mg Q2W/Lebrikizumab 250 mg Q2W	LEB250Q2W/PBO/LEB250Q2W; LEB250Q2W/ LEB250Q4W/ LEB250Q2W; LEB250Q2W/ LEB250Q2W/ LEB250Q2W; PBO/PBO/LEB250Q2W; PBO/LEB250Q4W/LEB250Q2W; PBO/LEB250Q2W/LEB250Q2W	No Between-Group or Overall Comparisons

Study Period	Analysis Population	Treatment Groups	Abbreviation	Inferential Comparisons When Applicable
Combined Induction and Maintenance Periods	All Lebrikizumab Modified Safety; All Lebrikizumab Safety	Any Lebrikizumab	N/A	No Between-Group or Overall Comparisons
Combined Induction and Maintenance Periods + FU	All Lebrikizumab Modified Safety; All Lebrikizumab Safety	Any Lebrikizumab	N/A	No Between-Group or Overall Comparisons

Abbreviations: FU = follow-up; ITT = intent-to-treat; LEB = lebrikizumab; NonResp = non-responder; PBO = placebo; Q2W = every 2 weeks; Q4W = every 4 weeks; Res = responder.

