6.16.1. Impact of COVID-19

Impact of pandemic (eg, COVID-19) on analyses may be addressed prior to study unblinding at Week 16 DBL, once the impact on study conducts are fully understood. In general, any missing assessments/visit window will be documented as protocol deviations. For patients who have missing assessments at Week 16 due to COVID-19, these patients may enter the escape arm. A summary or listing may be provided to summarize missing visits due to COVID-19.

Treatment discontinuation due to pandemic will be treated the same type of intercurrent event as treatment discontinuation due to reasons other than lack of efficacy. Strategies of how this type of intercurrent event will be handled are described in Section 6.2. Intermittent missing assessment due to pandemic will be treated the same as any other intermittent missing values. Details of how missing data will be handled are described in Section 6.4.

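### The Week 16 Escape groups are labelled NonResp, but entry also admits rescued patients in response and possibly COVID-missing patients, so their summaries do not estimate response among Week 16 non-responders

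*SAP*

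**What the plan says.** **Definition.** SAP Table KGAC.6.1 describes the Maintenance W16 Escape Population as patients not re-randomized to either lebrikizumab regimen "or placebo but assigned to escape arm at Week 16" who took at least one maintenance dose. The modified version only removes Site 5042. The neighbouring W24-48 Escape Population, by contrast, is defined by cause (loss of EASI-50).

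**Label.** Table KGAC.6.2 names one group "Placebo_NonResp/Lebrikizumab 250 Q2W" and the other correspondingly for lebrikizumab. Its footnote expands NonResp as non-responder.

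**Entry routes.**
- SAP 5.1.3.2 lists "Patients who do not achieve an IGA of 0 or 1 or an EASI-75 at Week 16" and, as a separate item, "patients received topical or systemic rescue therapy between baseline to Week 16".
- Protocol 5.3.3 has the same two routes: "Patients who require topical or systemic rescue treatment (Section 6.3) for atopic dermatitis during the Induction Period, or, are non-responders at Week 16".
- SAP 5.3 makes re-randomization "based on the IGA or EASI score at Week 16 and rescue therapy usage during induction period".
- SAP 6.16.1 adds: "For patients who have missing assessments at Week 16 due to COVID-19, these patients may enter the escape arm".

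**Responder.** SAP 5.1.3.1, the footnote to SAP Figure KGAC.5.1 and Protocol 5.3.2 define a responder by IGA 0/1 or EASI-75. None of them mentions rescue.

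**Reporting.** For this population Table KGAC.6.12 plans proportions with IGA 0/1, EASI-75, pruritus, sleep-loss and DLQI response at all scheduled maintenance visits. The rows are descriptive, with estimand NA and no split by route of entry. The Version 5 revision history explains why the population was added to the Section 6.8 summaries: "Added to allow the comparison between responders and non-responders at Week 16 in terms of patient characteristics".

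**The concern.** A table headed non-responder that follows IGA 0/1 and EASI-75 to Week 52 will be read as showing how many Week 16 non-responders go on to respond. In the lebrikizumab group that is response on continued treatment; in the placebo group it is response after starting active drug. A patient who was already in response at Week 16, and sits in the arm only because of induction rescue, can count as a response from the first escape visit without having gained anything after Week 16. A patient with no Week 16 assessment cannot be classed either way. Because the routes are pooled, a reader can recover neither the rate among true non-responders nor the number of other patients mixed in. The baseline summary meant to set responders beside non-responders is blurred in the same way.

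**Working it through.** **1. Follow one patient through the rules.** Take a patient who used topical rescue in induction and met EASI-75 at Week 16.

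| Place | Result |
|---|---|
| SAP 5.1.3.1, responder definition | Responder |
| SAP 5.1.3.2 and 5.3, allocation | Escape arm, because of rescue |
| Table KGAC.6.1, population | In the W16 Escape population |
| Table KGAC.6.2, label | NonResp |
| Table KGAC.6.12, first escape visit | Counts towards EASI-75 if the observed score still meets it |

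The first and fourth rows conflict, and the last row turns the conflict into a possible bias. The conflict follows from the text alone and needs no assumption.

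**2. Size of the group.** The plan gives no figure for the make-up or response rate of this population, so there is none to reproduce. The nearest inputs are the sizing assumptions in SAP 5.2: about 400 patients at 2:1, with Phase 2b EASI-75 rates of 48.0% and 11.5% that already count rescue as non-response.

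- Lebrikizumab: 400 × 2/3 = 267, and 267 × (1 − 0.480) = 139.
- Placebo: 400 × 1/3 = 133, and 133 × (1 − 0.115) = 118.

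If those rates hold, these are rough ceilings before any COVID-missing patients: dropouts never enter, and patients with IGA 0/1 but not EASI-75 are re-randomized unless rescued.

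**3. Size of the bias.** Let *f* be the share of the group that met, or would have met, response at Week 16. Let *rR* be the later response rate of those patients and *rN* that of the true non-responders.

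- Reported rate = (1 − *f*) × *rN* + *f* × *rR*
- Bias = *f* × (*rR* − *rN*)

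The documents give none of the three, so all values below are assumptions. With *rN* of 30% to 50% and *rR* of 75% to 90%, the smallest gap is 75 − 50 = 25 points and the largest 90 − 30 = 60. With *rR* of 20%, the gap is −10 to −30 points.

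| *f* | Bias, *rR* 75% to 90% | Bias, *rR* 20% |
|---|---|---|
| 2% | +0.5 to +1.2 points | −0.2 to −0.6 points |
| 5% | +1.25 to +3.0 | −0.5 to −1.5 |
| 10% | +2.5 to +6.0 | −1.0 to −3.0 |
| 20% | +5.0 to +12.0 | −2.0 to −6.0 |

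On 139 lebrikizumab patients, *f* of 2% to 20% is about 3 to 28 patients. If *rR* = *rN* the bias is zero.

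**4. Sign.** Protocol 6.3 stops study drug in induction only for systemic rescue, and it allows intermittent topical rescue in the Escape Arm. A response reached with topical rescue can therefore plausibly persist, which favours *rR* > *rN*. Systemic rescue points the other way: study drug was stopped and a washout precedes entry, so the response may be lost. The protocol gives no split between the two kinds of rescue.

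**The case against.** **The label follows the SAP's own convention.** The induction primary estimand (SAP 6.2.1.1) counts any rescued patient as a treatment failure, and SAP 5.3 uses rescue in allocation. In that sense a rescued patient is a non-responder at Week 16. This explains the label but does not settle the matter. The escape rows carry no estimand and no stated rule for rescue, so the same patient can be a non-responder at entry because of rescue and a responder at the next visit on the observed score.

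**Week 16 values will be visible.** SAP 6.1.3 presents Week 16 scores in the visit-wise maintenance reports unless otherwise specified, and SAP 6.1.3.3 speaks of maintaining as well as achieving response. This stands: it would be wrong to infer that patients already in response necessarily pass unseen. It is still a pooled starting point that does not give the rate among non-responders. The SAP also does not say whether rescued patients' Week 16 values appear there as observed.

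**The comparison of responders with non-responders is a rationale, not an analysis.** This also stands. SAP 6.8.1 plans a baseline summary by population without formal comparison unless otherwise specified. The revision history shows only the purpose for which the summary was added.

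**Nothing confirmatory depends on these tables.** Correct. Table KGAC.6.2 plans no comparison between the groups, and SAP 6.1.3.3 rules out inference.

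**Conclusion.** The mismatch between label and entry rules is established from the documents. The Table KGAC.6.12 summaries describe everyone sent to the arm at Week 16, not Week 16 non-responders.

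Three stronger readings are tempting and are not supported:

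- *That the rates certainly overstate response, by a known amount.* Overstatement is the likelier direction, but it requires *rR* > *rN*. The documents give neither rate and not the share *f*. The range of 0.5 to 12 points rests on the assumed values above, and −0.2 to −6 points is possible if response reached on rescue is lost.
- *That any patient with a missing Week 16 visit enters.* SAP 6.16.1 covers only assessments missing because of COVID-19, and its wording is permissive.
- *That the trial's conclusions are at risk.* No primary, major secondary or alpha-controlled result uses this population.

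The consequence is one of interpretation: a descriptive result open to misreading, with the information needed to correct it left out of the tables. A related but separate gap is that SAP 5.1.3.2 terminates patients without EASI-50 after 8 weeks in the arm, while the SAP states no denominator or missing-data rule for these summaries. If observed cases are used, the share of patients already in response at entry could grow over time.

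**What to change.** Change the reporting only; allocation and patient management stay as they are.

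1. In Tables KGAC.6.1 and KGAC.6.2, relabel the two groups W16 Escape.
2. Report counts, by induction arm, cross-classified by reason for entry (Week 16 non-response, induction rescue, Week 16 assessment missing because of COVID-19) and by observed Week 16 response status (met, not met, missing).
3. In the W16 Escape summaries of Table KGAC.6.12 and in the Section 6.8 baseline summary, keep the total and add a row or column restricted to patients with an observed Week 16 assessment who met neither IGA 0/1 nor EASI-75. Use NonResp only for that subset. Rescued patients who met neither criterion belong in it.

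In the restricted rows *f* = 0, so this bias disappears whatever the values of *rR* and *rN*. The cost is one derived flag, a few more columns and a slightly smaller denominator in the restricted rows.

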6.1.2. General Considerations for Analyses During Induction Period

Induction Period starts after the first injection of study treatment at Baseline Visit (Day 1) and ends prior to the first injection of study treatment at Week 16 or the early termination visit (ETV) (between Day 1 and Week 16). For patients who are randomized but not dosed, the Induction Period starts on the date of randomization.

Baseline will be defined as the last available value before the first injection for efficacy and health outcome analyses. In most cases, this will be the measure recorded at Baseline Visit (Day 1). If the patient does not take any injection, the last available value on or prior to randomization date will be used. Change from baseline will be calculated as the visit value of interest minus the baseline value.

For Pruritus Numeric Rating Scale (NRS) and Sleep-Loss due to Pruritus collected via eDiary, the baseline period is the 7-day window prior to the first injection. A patient must have responses on at least 4 of 7 days to calculate a baseline weekly mean. If a patient has 3 or fewer responses, the baseline mean value will be considered missing. eDiary data for Pruritus NRS and Sleep-loss due to Pruritus are mapped to study visit per [Appendix 1](#).

For the safety analyses, the following baselines will be used. For safety analyses using a baseline period, the baseline period is defined as the time from Screening Visit to the date/time of the first injection in Induction Period.

- Treatment-emergent adverse events (TEAEs): baseline will be all results recorded during the baseline period.
- Treatment-emergent abnormal laboratory and vital signs results: baseline will be all results recorded during the baseline period.
- Change from baseline to last post-baseline observation or to each scheduled post baseline visit for laboratory and vital signs results: baseline will be the last scheduled non-missing assessment recorded during the baseline period.

The randomization to treatment groups is stratified by geographical region (US versus EU versus rest of world), age (adolescent patients 12 to <18 years versus adults ≥ 18 years) and baseline disease severity (IGA 3 versus 4) as described in Section [5.3](#). The countries will be categorized into geographic regions for analysis (Section [6.3](#)). Unless otherwise specified, the statistical analysis models for Induction Period will adjust for geographic region, age and baseline disease severity.

For assessments of the primary endpoints and other binary efficacy and health outcomes endpoints, the following will be provided:

- Crude proportions for each treatment group along with the 95% two-sided asymptotic (ie, not continuity corrected) confidence intervals (CIs) will be provided.

- The estimated common risk difference along with 95% CIs. The common risk difference is the difference in proportions adjusted for the stratification factors as mentioned in Section 6.3. SAS® PROC FREQ will be used for the estimates and CIs, where the CIs are calculated by using Mantel-Haenszel-Sato method (Sato 1989).
- Cochran-Mantel-Haenszel (CMH) test will be used to compare the treatment groups while adjusting for the stratification factors. The CMH p-value will be reported, and the CMH adjusted odds ratio along with the 95% two-sided asymptotic (ie, not continuity corrected) CIs.

Treatment comparisons of key continuous efficacy variables and health outcome variables at each postbaseline time point will be made using analysis of covariance (ANCOVA) with the following in the model: treatment group, baseline value, and stratification factors mentioned in Section 6.3. Type III tests for least squares (LS) means will be used for statistical comparison between treatment groups. The LS mean difference, standard error, p-value, and 95% CI, unless otherwise specified, will also be reported.

Treatment comparisons of other continuous efficacy variables and health outcome variables with multiple postbaseline measurements will be made using mixed-model for repeated measures (MMRM). When MMRM is used, the model includes treatment, baseline value, visit, the interaction of the baseline value-by-visit, the interaction of treatment-by-visit, and the stratification factors mentioned in Section 6.3 as fixed factors. The covariance structure to model the within-patient errors will be unstructured. If the unstructured covariance matrix results in a lack of convergence, the heterogeneous Toeplitz covariance structure, followed by the heterogeneous autoregressive covariance structure will be used. The restricted maximum likelihood (REML) will be used. The Kenward-Roger method will be used to estimate the denominator degrees of freedom. Type III tests for the LS means will be used for the statistical comparison; the 95% CI will also be reported.

For variables that are not collected at each postbaseline visit, data may exist at visits where the variable was not scheduled to be collected. In these situations, data from the early discontinuation visit that do not correspond to the planned collection schedule will be excluded from the MMRM analysis (Andersen and Millen 2013). Also for by-visit summaries/displays such as boxplots, the weeks when data was not scheduled to be collected may not be displayed. However, unscheduled assessments within any defined study period will still be used in the shift analyses, and for imputing values for the change from baseline to last observation carried forward (LOCF) endpoint analyses.

The Kaplan-Meier (KM) product limit method maybe used to estimate the survival for time to event analyses. The log-rank test stratified by the stratification factors mentioned in Section 6.3 will be reported. A Kaplan-Meier plot of the time to event by treatment group may be provided.

Unless specified otherwise, Fisher's exact test will be used for adverse events (AEs) and other categorical safety measures. Odds ratios will be created with lebrikizumab treatment as the numerator, and placebo as the denominator. Continuous vital sign and laboratory values will be analyzed by an ANCOVA with treatment and baseline value in the model.

